**NCT number: NCT05570500**

**Date of document: November 21st, 2020**

## **1. Background:**

Caries is one of the greatest challenges facing the health system in Egypt, and as of the past few years studies have shown that Egyptian children have many dental problems, including: untreated dental caries, forms of periodontal diseases and even irregular tooth brushing habits. The latter being mainly due to the ignorance of children of understanding the correct technique of tooth brushing, which may have been due to the lack of dental awareness that these children receive, either by dental professionals who should offer this service regularly [1] or due to poor parental awareness of the factors that affect the oral health status of their children [2].

Oral health (OH) education has proven to play a significant role in improving the knowledge, attitude and behaviour of children [3]. Implementing Oral health education in schools tend to improve the children's OH-related quality of life because engaging children at younger age regarding their habits, practices or knowledge tends to stay with them till adolescence then to adulthood [4].

In the year 2019 the Covid crisis has globally struck, being recognised by the WHO as a pandemic on March 11th, 2020 [5] the world was set in motion for various changes in the daily life of every man, woman and child. Covid 19, as defined by the WHO, is an infectious disease that spreads through droplets of saliva or discharge from the nose when the infected person sneezes or coughs, and thus the best way to avoid being infected by this disease is through some precautions that include social distancing of at least 1-2 meters between each person [6]. In Egypt, 75% of school children are usually very crowded in classrooms, which sometimes might reach 40 students per classroom or even more in certain schools [7]. Such numbers pose a great challenge to fulfilling the Covid precautions set by the WHO.

Luckily, we are in an era of technological advancement and the need for the electronic communication has risen to its peak. Recently, Egyptian ministry of education had applied the online education system as a must have in all schools and even released an online governmental portal which provides E-learning service, which in turn, would allow the students to remain at home while receiving their education [8]. Oral health education, which is considered as a part of the health promoting schools according to the WHO [9], has been known to be effective at

direct contact between the educator and the recipients [10], and many modifications in the way of delivering knowledge to children has been improved to include games, drama scenes and flash cards [11]. The challenge nowadays is that with the Covid outbreak the need for more distancing and less direct contact between people has increased, and the conventional methods of health education might deem unfit towards the global direction to control the Covid outbreak.

The online methods of delivering oral health education has been shown to be effective using Motivational Interviewing (MI) [12]. MI, defined by Miller & Rollnick (2002) as a technique based on evidence, centred on the individual, and individually-tailored. This technique is meant to prepare the participant for change by motivating and promoting the participant's solutions to the inconsistency of decisions towards self-improvement [13]. Few studies have engaged young adolescents through MI [14], yet with young children the MI results are still under investigation [15]. With the Covid outbreak still on the loose, oral health educators must follow the guidelines presented by the WHO to prevent its spreading all the while providing oral health education service to school children. Hence finding ways to implement the oral health education into the online education system is challenging yet an important step to address young children in these hard times, in order to help them understand how to take care of their oral hygiene while keeping them, their families and their environment safe from harm.

2. **Research question:** is the online method of delivering oral health knowledge to primary school children is as effective as the conventional methods regarding their knowledge and practice towards personal oral hygiene?

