**Objectives:**

➤ **Primary objective :**

- To compare the online oral health education to the conventional oral health education regarding :
  1. Oral health knowledge of primary school children of 7-9 years old.
  2. Assessing oral hygiene measures practice in primary school children of 7-9 years old.

➤ **Secondary objective :**

Is to evaluate the efficacy of a new oral health education method to deliver health information to target population

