**Study hypothesis:****▪ Null hypothesis:**

No difference between the effectiveness of online oral health education and conventional oral health education methods on oral health knowledge and oral hygiene practice of primary school children

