### **Sample size calculation:**

Sample size estimation was based on testing the change in KAP before and after each educational intervention. The predicted sample size was found to be 265 children for each intervention, by assuming an  $\alpha$  level of 0.05,  $\beta$  level of 0.1 (power = 90%), allocation ratio of 1:1, to detect an effect size  $d$  of 0.2. After adding a 20% increase to adjust for dropout, the final sample size was 318 children for each intervention (total sample size = 636 children). Sample size calculation was performed using G\*Power software version 3.1.9.4 for MS Windows, Franz Faul, Kiel University, Germany.

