### **Study procedures:**

- 1) A literature review was conducted using electronic search engines like PubMed and Google scholar to identify studies assessing the effect of online and conventional oral health education on improving the oral health knowledge and practice in school children regarding their oral hygiene.
- 2) After reviewing many articles, a questionnaire was selected to assess the above outcomes. The questionnaire was chosen according to availability and effectiveness, and it was modified by simplifying and deselecting some of the questions that aren't related to the age group to better suit the age group of question.
- 3) A piloting session will be done on two separate classes, one from each educational stage to assess the modified questionnaire in terms of ease of understanding and comprehension to the participants. Those two classes will not be included in the final results of the study.
- 4) The questionnaire will be distributed before conducting the oral health education sessions (both online and conventional) to assess the pre-session knowledge and practice of the participants.
- 5) All questionnaires are self-administered but a well-trained interviewer will be available offering assistance in understanding the questionnaires if needed.
- 6) 3rd and 4th grade classrooms in each school will be randomly and evenly allocated to the interventions included in the study using computer-generated randomization application.
- 7) The researcher will be blinded of the classrooms of each school during the randomization process.
- 8) The researcher will be blinded of the names of the participants or their personal data during and after the questionnaire session.
- 9) After the questionnaire is finished, the researcher will then begin his educational lesson using electronic aids like a projector inside the classrooms or using Microsoft teams during the online session.
- 10) Another questionnaire will be distributed after the educational lesson for both session types to assess the post-session knowledge and practice in the participants.
- 11) A comparison will be carried out for the results of each question in both questionnaires and for the final results of both questionnaires to determine the statistical significance of both results.
- 12) These statistical results will be done by a separate statistician outside the study field and blinded from all the procedures.

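### The protocol asks whether online education is as effective as conventional education, but its only hypothesis is a null of no difference with no margin, so a non-significant between-arm result cannot answer the question

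*Protocol*

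**What the plan says.** Section 2 of the protocol (Research question) asks "is the online method of delivering oral health knowledge to primary school children is as effective as the conventional methods", with regard to knowledge and practice of oral hygiene.

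Under Study hypothesis the protocol gives one statement, a null: "No difference between the effectiveness of online oral health education and conventional oral health education methods". It states no alternative hypothesis, no non-inferiority or equivalence margin, and no rule based on a confidence limit, there or elsewhere.

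The Aim and the primary objective are neutral. The objective is "To compare the online oral health education to the conventional oral health education regarding" knowledge and practice.

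Step 11 of Study procedures plans comparisons question by question and "for the final results of both questionnaires to determine the statistical significance of both results". Section 6 leaves the analysis to a statistician once all data are in.

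The sample size is not built on the between-arm comparison: "Sample size estimation was based on testing the change in KAP before and after each educational intervention". It gives 265 children per intervention, raised to 318 for dropout.

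**The concern.** The question and the hypothesis do not match. If the question is whether online is as good as conventional, a favourable answer amounts to the null hypothesis. A test of that null can reject it but cannot confirm it, because failing to reject is also what a small or noisy trial produces when a real difference exists.

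What is at stake is the conclusion drawn when the arms do not differ significantly. The Background presents conventional teaching as possibly unsuitable under Covid distancing, with online delivery as the alternative, so this outcome matters in practice. Without a margin or a reporting rule, nothing in the protocol separates a trial that has excluded an important deficit from one that was too imprecise to see it.

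**Working it through.** **Inputs from the protocol (Sample size calculation):** alpha 0.05, power 90%, allocation 1:1, effect size 0.2, 265 per intervention, 318 after a 20% increase. Sidedness is not stated; two-sided is assumed because it reproduces the figure.

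**Assumptions not in the protocol:** a true between-arm deficit of 0.2 SD of the score compared; ICC of 0.02 or 0.05; 40 children per class. The Background mentions 40 as a number that Egyptian classes sometimes reach, not as the size of this trial's classes.

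**1. Reproduce the plan's figure.** For a paired comparison, n = ((1.960 + 1.282)/0.2)² = 263 by the normal approximation. With the noncentral t the smallest n is 265 (power 0.9004), and 265 × 1.20 = 318. Both stated figures reproduce. A two-sided independent two-sample t-test at the same effect size would need 527 per arm. So 265 is a within-arm, before/after figure.

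**2. How often a difference test would miss a real deficit.** With 265 per arm, SE = √(2/265) = 0.0869 SD.
- True deficit 0.2 SD: 0.2/0.0869 = 2.30; power ≈ Φ(2.30 − 1.96) = 0.63 (noncentral t: 0.632). Non-significant: 1 − 0.632 = 0.368, about 37%.
- The same deficit with 318 per arm (no dropout): power 0.712, non-significant about 29%.
- True deficit 0.1 SD with 265 per arm: non-significant about 79%.

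**3. What an observed difference of zero would show.** 95% CI half-width = 1.96 × 0.0869 = 0.17 SD with 265 per arm. Deficits of up to about 0.17 SD would remain compatible with the data.

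**4. Effect of clustering.** Step 6 of Study procedures allocates classrooms, not children. Design effect = 1 + (40 − 1) × ICC.

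| ICC | Design effect | Effective n per arm | Non-significant if 0.2 SD worse | 95% CI half-width |
|---|---|---|---|---|
| 0 | 1.00 | 265 | 37% | 0.17 SD |
| 0.02 | 1.78 | 149 | 59% | 0.23 SD |
| 0.05 | 2.95 | 90 | 73% | 0.29 SD |

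**5. What a margin would require** (one-sided 0.025, 90% power, true difference zero, no clustering).
- Smallest margin that 265 per arm supports: (1.960 + 1.282) × 0.0869 = 0.28 SD. With 318 per arm it is 0.26 SD.
- n per arm = 2 × ((1.960 + 1.282)/margin)²: 934 at 0.15 SD, 526 at 0.20 SD, 337 at 0.25 SD, 234 at 0.30 SD.
- At a margin of 0.20 SD, 265 per arm gives 63% power.
- With the effective sizes in step 4, the smallest margin becomes 3.242 × √(2/149) = 0.38 SD at ICC 0.02, and 3.242 × √(2/90) = 0.48 SD at ICC 0.05.

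The margins are illustrations; the protocol names none.

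**The case against.** The strongest reply is that this is one loosely worded sentence. The Aim, the primary objective and the null all describe a neutral comparison, and the phrase in the research question may be everyday language. That is a fair point. It makes rewording the natural remedy, but it does not remove the conflict between the question and the hypothesis.

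Four stronger readings are tempting and are not supported:
- A reader might infer that the sponsor will treat a non-significant result as proof of equal effectiveness. No section says so. The protocol simply does not rule it out.
- A reader might infer that no result could answer the question favourably. That goes too far: a significant advantage for online would support a favourable answer, and a significant deficit would answer it unfavourably. The gap is the no-difference outcome.
- A reader might take 0.2 SD as the between-arm difference the plan wants to detect. It is the within-arm before/after effect size, so its use here as a between-arm deficit is an assumption.
- A reader might take step 11 of Study procedures as the between-arm significance test. Steps 4 and 10 define a pre-session and a post-session questionnaire, so step 11 can equally be read as a before/after comparison. The point does not depend on it.

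A statistical analysis plan that is not at hand might set a margin. The protocol's own question and hypothesis would still disagree. Finally, a margin guards against imprecision only. Contamination or an insensitive questionnaire would shrink the observed difference and could favour a non-inferiority claim too.

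**Conclusion.** The mismatch is in the text and needs no assumption: the question is one of equal effectiveness, the only hypothesis is a null of no difference, and there is no margin or confidence-limit rule. As written, a non-significant between-arm result cannot support a conclusion that online is as effective.

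The size of the risk is illustrative. Under an assumed true deficit of 0.2 SD, a two-sided 5% test and 265 independent children per arm, that result would occur about 37% of the time. The 59% and 73% figures also rest on the assumed class size and ICCs; they show the direction of the clustering effect and are not estimates for this trial.

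**What to change.** **Preferred change.** Reword the research question as whether the two methods differ in their effect on knowledge and practice, in line with the Aim, Objectives and Study hypothesis. Add that the between-arm difference will be reported with a 95% CI adjusted for classroom clustering, and that a non-significant result will be described as inconclusive and not as equal effectiveness. This costs a few sentences and no extra children. The downside is that equal effectiveness can no longer be claimed from a p-value above 0.05.

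**Alternative, if the sponsor wants to keep its question.** Pre-state and justify a margin on the primary score, replace the null with one that online is worse by at least that margin, and claim non-inferiority only if the confidence limit of the between-arm difference excludes it. If equivalence is intended, limits on both sides are needed. The power must then be restated for the between-arm comparison with clustering. This option is a real trade-off: 265 per arm reaches 90% non-inferiority power only for a margin of about 0.28 SD or wider before clustering, and a 0.20 SD margin would need 526 per arm before clustering and dropout. The choice of margin is for the investigators and should be made before any data are seen.

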**Framing the research question - PICOTS:**

P (participants): Primary school children of ages 7-9 years old in Egypt.

I (intervention): Online oral health education.

C (comparator): Conventional oral health education.

O (primary outcome): Improving the oral hygiene knowledge and practice in primary school children.

T (Time of follow up): Every 3 months interval for one academic year.

S (Study settings): 2 schools will be chosen (Al Rehab city and Al-Sherook city). The rationale behind choosing those two schools is to increase the sample size. Classrooms of grade two and grade three stages inside each school will be divided blindly into two groups; one receives the online oral health education while the other receives the conventional oral health education. Both schools had received simplified conventional oral health education service two years ago. The participants were of 5-6 years of age by then.

**3. Aim:**

The aim of this study is to compare the results of the comparison between the online oral health education and conventional oral health education methods in terms of their effectiveness towards improving the knowledge and practice of oral hygiene in primary school children in Egypt.

**Objectives:**

➤ **Primary objective :**

- To compare the online oral health education to the conventional oral health education regarding :
  1. Oral health knowledge of primary school children of 7-9 years old.
  2. Assessing oral hygiene measures practice in primary school children of 7-9 years old.

➤ **Secondary objective :**

Is to evaluate the efficacy of a new oral health education method to deliver health information to target population

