**4. Methods:**

- **Study design:** Randomized controlled trial (RCT)
- **Study settings:** 2 schools will be chosen (Al Rehab city and Al-Sherook city). The rationale behind choosing those two schools is to increase the sample size. Classrooms of grade three and grade four stages inside each school will be divided blindly into two groups; one receives the online oral health education while the other receives the conventional oral health education. Both schools had received simplified conventional oral health education service two years ago. The participants were of 5-6 years of age by then.
- **Study population:** Grade three and grade four Egyptian students aged 7-9 years old situated in 2 different schools related to Futures Educational Systems in Egypt.

Inclusion criteria	Exclusion criteria

 
• 2nd and 3rd grade Egyptian students.
 
• Average of age 7-9 years old.
 
• Currently residing in Egypt.
 
• Both male and female students.
 
	
 
• Those who do not consent to participate in the study.
 
• Those who cannot speak English or Arabic.
 
• Non-Egyptians.
 

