**Ethical consideration:**

All participants' parents will be briefed about the nature of the study and an **informed consent form** will be delivered to them both in Arabic and English languages for their approval to include their children's data in the study. This informed consent will be available and approved by the Ethical Committee of Faculty of Dentistry, Ain Shams University. There will also be an assent from each child to freely accept or decline joining the study prior to the questionnaire. Parents and/or children will be given the complete freedom to complete or quit the study whenever they want. Also, they will be assured of the confidentiality of their personal information and anonymity. The participants who won't participate in the study or are excluded will receive the oral health education in both methods (online and conventional) nonetheless as it is ethically not appropriate for one person to receive the health education service while the other doesn't in the same working / studying space.

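### The secondary objective asks for the efficacy of the new method, but both arms are educated and the sized test is before-after, so a significant change cannot be credited to the lesson

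*Protocol*

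**What the plan says.** The Objectives section of the protocol lists a primary objective, which compares online with conventional education on knowledge and practice, and then a separate secondary one: "Is to evaluate the efficacy of a new oral health education method to deliver health information to target population". From the context, the new method is the online one.

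The design gives this objective no uneducated reference:

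- PICOTS names an active comparator: "C (comparator): Conventional oral health education".
- Under 4. Methods, classrooms are split into two groups: "one receives the online oral health education while the other receives the conventional oral health education".
- Under Ethical consideration: "The participants who won't participate in the study or are excluded will receive the oral health education in both methods (online and conventional) nonetheless".

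On the test, the section on sample size states: "Sample size estimation was based on testing the change in KAP before and after each educational intervention", and then "The predicted sample size was found to be 265 children for each intervention". Study procedures has a questionnaire before the session (step 4) and one after it (step 10): "Another questionnaire will be distributed after the educational lesson for both session types". Step 11 compares the two questionnaires, item by item and in total, for statistical significance. The only null hypothesis stated is of no difference between the online and conventional methods.

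**The concern.** Efficacy in its own right means that the lesson caused the improvement. The only randomised contrast here is online against conventional education, which shows whether one method does better than the other. It does not show whether either does better than no lesson.

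The analysis that lies closest to hand for the secondary objective is the before-after change in the online arm, because that is the test the protocol sizes and describes. A child's score may rise the second time because the questions are familiar. At the follow-ups that PICOTS plans every three months over an academic year, it may also rise because the child is older. A before-after test counts all of this as change. If a significant result were reported as efficacy, the trial would make a public claim about the online method with no controlled evidence behind it.

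**Working it through.** **1. Which test was sized?** Inputs from Sample size calculation: alpha 0.05, power 90%, d = 0.2, 265 per intervention. Sidedness is not stated, so both were tried.

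- Paired t-test, two-sided, normal approximation: n = ((1.960 + 1.282) / 0.2)² = 262.7, so 263. The exact noncentral-t calculation gives **265**, the protocol's figure. Adding 20% gives 265 × 1.2 = 318, also as stated.
- Paired t-test, one-sided: 216.
- Two-sample comparison of the arms, two-sided: 526 per arm (normal approximation) or 527 (exact t). One-sided: 429.

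Only the two-sided paired test reproduces 265. The arithmetic agrees with the text: the sized test is the change within an arm.

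**2. What that test measures.** For one arm,

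mean change = lesson effect + retest gain + effect of time.

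The before-after test rejects when this sum differs from zero, whichever term is responsible. In the difference between arms, retest and time terms common to both cancel, leaving the online lesson effect minus the conventional one.

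**3. Illustration: no lesson effect, only a retest gain.** The gain d is in units of the standard deviation of the change and is an assumption. Children are treated as independent. The probability of two-sided significance is that of a noncentral t with n − 1 degrees of freedom and noncentrality d√n.

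| Retest gain d | d√265 | P(significant), n = 265 | P(significant), n = 318 |
|---|---|---|---|
| 0 | 0 | 0.05 | 0.05 |
| 0.05 | 0.81 | 0.13 | 0.14 |
| 0.10 | 1.63 | 0.37 | 0.43 |
| 0.15 | 2.44 | 0.68 | 0.76 |
| 0.20 | 3.26 | 0.90 | 0.94 |

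**4. The randomised contrast under the same gain.** In 20,000 simulated trials with 265 per arm and the same gain in both arms, the two-sample test rejected in 5.0% of trials (d = 0.1) and 5.1% (d = 0.2). The nominal level is kept.

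**5. Power of that contrast at the planned size.** For a between-arm d of 0.2, the noncentrality is 0.2 × √(265/2) = 2.30, and the exact two-sided power is 0.63. If all 318 per arm were analysed it would be 0.71. Neither figure allows for classroom allocation or baseline adjustment.

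**The case against.** The strongest reply is that the protocol never ties the secondary objective to the before-after test. The objective names no endpoint, test or decision rule, and an analysis plan that is not shown may supply one. The research question, aim, primary objective and null hypothesis are all comparative, so efficacy may mean efficacy relative to conventional education, which the design can address. This stands in part. A reader might infer that the protocol commits itself to declaring efficacy from a significant within-arm change, but no such rule is written. Even so, an analysis plan cannot add an uneducated reference, and the only test sized in the protocol is the uncontrolled one. On the relative reading, the objective largely repeats the primary one, and the sample size was not set for it.

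Three further inferences are tempting and are not supported:

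- **Interviewer help inflates the later score.** Step 5 of Study procedures makes help available for all questionnaires, so before and after alike.
- **A year of growing older affects the comparison around the lesson.** Steps 4, 9 and 10 describe a questionnaire, the lesson and another questionnaire. Maturation matters for the later follow-ups in PICOTS.
- **The 0.90 is an expected false-positive rate.** It is the planned power, which arises because the largest assumed gain equals the design effect. No document says that a retest gain of that size will occur.

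It is also fair to say that identical items are not stated. Step 10 speaks only of another questionnaire, and matched items are inferred from the question-by-question comparison in step 11.

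**Conclusion.** The point holds in a limited form. A significant before-after change in this trial cannot be attributed to the lesson, and the secondary objective as worded invites that attribution.

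The size depends on a quantity the protocol does not give. Over an assumed pure retest gain of d = 0.05 to 0.20, with independent children and n = 265, the sized test would be significant with probability 0.13 to 0.90 instead of 0.05. These figures show how sensitive the test is to a modest artefact; they do not forecast one.

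A reader might infer that the randomised comparison is compromised as well, or that an uneducated arm is required. Neither follows. A gain common to both arms cancels in the between-arm difference. That it is common is itself an assumption, since Data management lets the questionnaire format follow the type of session. The protocol also gives an ethical reason for educating everyone, and the problem can be met without an uneducated arm.

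**What to change.** - **Objectives:** reword the secondary objective either as the effectiveness of online education relative to conventional education, or as a description of the change within each arm. The first option overlaps with the primary objective; the second does not.
- **Objectives, Sample size calculation and Study procedures step 11:** state that significance of a within-arm before-after change will not be used to claim efficacy, and that conclusions rest on the between-arm difference adjusted for the baseline score.
- **Sample size calculation:** state that 265 per arm was set for the before-after test and gives about 63% power for a between-arm d of 0.2, before any allowance for classroom allocation (which would tend to lower it) or baseline adjustment (which would tend to raise it).

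No arm is added, and the commitment to educate every child who declines or is excluded stays as it is. The cost is more than wording. The sponsor gives up the absolute efficacy claim. Once the before-after change is descriptive, the 265 no longer belongs to an inferential test, so the protocol must either accept the lower power openly or revisit the sample size; an unadjusted between-arm test at 90% power would need 526 to 527 per arm.
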